⁹ Diary concordance training (takes approx. 2.5 hours). Could be done either at the screening visit or during a separate scheduled visit after receipt of the screening lab results and prior start of the baseline diary completion period.

Confidential	Version: 5.0	Page 15 of 74
Protocol: IRL790C005	Date: 5 Mar 2021	C C

¹ Safety follow-up visit to be performed (if possible) for early IMP discontinuations (5-8 days after last dose of IMP)

² Site to call the patient the working day before the first 24-hour diary completion period, as a reminder, and the working day after the last 24-hour diary completion period to encourage compliance.

³ CYP2D6 genetic informed consent must be signed prior CYP2D6 blood sample testing. Note: the CYP2D6 testing is optional

⁴ Triplicates separated by at least one minute

⁵ If 29 days or more between the Screening visit and Visit 1 (Baseline), safety parameters (Vital Signs, single ECG, Haematology/Clin Chem and Urinalysis) are included also at Visit 1 (Baseline).

⁶ Serum hCG; Only applicable for women with childbearing potential (as defined in section 8.1)

^{6a} Urine hCG; Only applicable for women with childbearing potential (as defined in section 8.1)

⁷ Part 4 question 4.2

⁸ Part 2 (M-EDL) and part 4 questions 4.1 and 4.2

Visit	Screening	Phone calls	Visit 1 (Baseline)	Visit 2	Phone call	Phone calls	Visit 3	Phone calls	Visit 4	Phone calls	Visit 5 (EOT)	Visit 6 (EOS/EW)
		Baseline diary period	Dose run-in				Treat	nent period	l			Follow up
Day	-56 to -10	-9 to -1	Day 1	9	14	21	28		56		84	
Week				Week 1	2	3	4	7	8	11	12	5-8 days after EOT
Time window	-	_2	-	+ 2 days	±2 days	± 2 days ²	± 4 days	_2	± 4 days	_2	-2 to 0 days	
24-hour patient home diaries hand out/collection	X ¹⁰		X ^{10 11}				X ^{10 11}		X ^{10 11}		X ¹¹	
24-hour patient home diary entry ¹²		Х				Х		Х		Х		
Patient motor function review							Х					
Modified UDysRS			Х				Х		Х		Х	
MMSE	X										Х	
CGI-S			Х				Х		Х		Х	
C-SSRS			Х				Х		Х		Х	
Adverse Event (AE)	Х	Х	Х	Х	Х	Х	Х	Х	Х	Х	Х	Х
Serious Adverse Event (SAE) collection/reporting	Х	Х	Х	Х	Х	Х	х	Х	Х	Х	Х	Х
Randomization ¹³			Х									
PK sample ¹⁴									Х		Х	
Dispense IMP			Х	Х			Х					
Collect empty bottles of IMP				Х			X ¹⁵		Х		Х	
Compliance				Х	Х	Х	Х	Х	Х	Х	Х	

Confidential	Version: 5.0	Page 16 of 74
Protocol: IRL790C005	Date: 5 Mar 2021	C

¹⁰ Three empty diaries handed out

¹¹ Three completed diaries collected

 ¹² Three completed diaries conjected

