In the MAD part of this study, 23 subjects were treated with IMP. In the first cohort, 9 subjects received mesdopetam, 40 mg/day for 10 consecutive days and 3 subjects received matching placebo. In the second cohort, 9 subjects received mesdopetam, 80 mg/day for 10 consecutive days and 3 subjects received matching placebo.

Overall, mesdopetam was well tolerated when given to healthy male subjects at single doses up to 120 mg and at multiple doses of 80 mg per day for 10 days. The maximum tolerated dose was set to 120 mg as a single dose and the maximal dose for multiple dosing was set to 80 mg per day. Most of the Treatment Emergent Adverse Events (TEAEs) (74%) were of grade 1 intensity while 26% were of grade 2 intensity. Most AEs (48%) reported were considered as not related to study treatment while 11% were possibly related and 41% probably related. Overall TEAEs were mild, transient and possibly CNS related.

In agreement with preclinical findings, the PK evaluation in humans showed dose-linear kinetics with rapid absorption (average $T_{max} \approx 1$ h) and log-linear decline with a plasma half-life around 7h. Urine recovery data confirmed elimination from plasma occurred by a combination of renal excretion (fractional excretion around 35%) and metabolic degradation.

Confidential	Version: 5.0	Page 28 of 74
Protocol: IRL790C005	Date: 5 Mar 2021	e

IRL790C002 (Phase 1b)

In the Phase 1b study (IRL790C002), 15 patients with advanced PD experiencing LID were randomized to receive mesdopetam or placebo (3:1 randomization) as adjunct treatment for 28 days. During the first two weeks of treatment, dosing was gradually increased until signs of intolerability occurred after which dose adjustments were made. Following this titration period, the dosing was kept stable for the remaining two weeks.

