Patients included in the study must be on stable antiparkinsonian medications for at least 30 days prior to first 24-hour patient home diary completion and during the study. Rescue medications such as Madopar dispersable and intermittent Apomorphine injections are allowed if prescribed PRN prior to study entry. Other medications considered necessary for the patient's safety and well-being may be given at the discretion of the Investigator.

All concomitant therapy used within the four weeks prior to the screening period and during the study must be recorded on the CRF.

Non-permitted concomitant medication:

Inbrija (levodopa inhalation powder) is not allowed as a rescue medication during the study. No other drug under investigation may be used concomitantly with the IMP.

Treatment with amantadine is not allowed within 6 weeks before completion of the first 24-hour patient home diary and during the study.

Available *in vitro* data indicate that CYP2D6 and CYP1A2 are the main enzymes involved in the metabolism of mesdopetam. However, the exact contribution from each of these two enzymes in the elimination is not known, and there may be a risk for significant increase of exposure when mesdopetam is used together with a combination of medications being strong inhibitors of CYP2D6 and CYP1A2 (see Table 1). Therefore, a combination of such inhibitors, i.e. a CYP1A2 strong inhibitor and a CYP2D6 strong inhibitor concurrently, should be avoided throughout the study. A CYP2D6 genotyping testing will be performed at Visit 4 (Day 56).

Mesdopetam and its two main plasma metabolites M1 (IRL902) and M2 (IRL872) have been shown *in vitro* to not be inhibitors of the main drug metabolizing CYP450 enzymes to a significant degree. Restrictions on concomitant medications being CYP450 substrates are therefore not considered necessary during the study.

Mesdopetam and metabolite M2 (IRL872) are also not inhibitors or substrates to a significant extent to main drug membrane transporters. Restrictions on concomitant medications being substrates or inhibitors of drug transporters are not considered necessary during the study.

Confidential	Version: 5.0	Page 38 of 74
Protocol: IRL790C005	Date: 5 Mar 2021	e

Isoenzyme (cytochrome P450)	Strong Inhibitors	
CYP1A2	ciprofloxacin, enoxacin, fluvoxamine, zafirlukast	A combination of a CYP1A2 inhibitor and a CYP2D6 inhibitor is not permitted during the study.

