The IRS will manage the randomization, stratification and IMP inventory supply chain. IRS will deliver the IMP at the correct time for both new and existing patients. IRS will also support the dosing schedules and will be used to track patient activities in real time throughout study visits. Real-time web reports and alerts platform (such as email and fax) give access to compliance feedback for continuous transparency of study progress. Patient unblinding is also contained within the IRS system to allow the unblinding of patients for safety purposes within the protocol via web or phone. If emergency unblinding is required, this responsibility lies solely with the Investigator. Unblinding for other safety purposes will be managed per Sponsor outlined request. Unblinding access can be controlled within the IRS by role type allowing only the appropriate role to unblind the appropriate patient.

Confidential	Version: 5.0	Page 42 of 74
Protocol: IRL790C005	Date: 5 Mar 2021	C

Prolactin Results

Minor increases in prolactin levels may be present in participants randomized to mesdopetam. It should be noted that this elevation in prolactin is not expected to be clinically significant but could be potentially detectable if comparing Visit 5 (EOT) results to screening. For this reason, prolactin is not included in the safety lab measurements at Visit 4 and laboratory analysis results for the prolactin value at Visit 5 will be blank (i.e. not revealed to the Investigator).

PK Samples

The laboratory analysing the PK samples will have access to the randomization list; only samples taken from patients in the active group of the study will be analyzed. Results of PK analysis will not be linked to patient number until the database is locked.

Breaking the Blind

Mesdopetam and placebo (capsules of identical appearance.) will be dispensed in identical containers according to a blinded randomization scheme. Study patients, Investigators, study staff and the Sponsor will remain blinded to the randomization scheme until the blind is formally broken for all patients. For this to occur all patients must have completed the study and the study database must be locked.

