4 SAMPLE SIZE

Analysis of the Phase IIa study Efficacy and Tolerability of IRL790 in 74 PD patients with levodopa-induced dyskinesia (LID) on stable antiparkinsonian medication (NCT03368170) suggested that daily ON-time with troublesome dyskinesia decreased to an observed difference of approximately 1.6 hours (p=0.0274) among treated patients (n=39) versus placebo (n=36). Doseresponse analysis suggested a dose dependent effect with an observed difference vs. placebo around 4.6 h at the 7.5 mg dose. A pooled standard deviation of 3.2-3.3 hours was observed among the doses studied. This observed data provided the assumptions for the sample size calculation.

140 randomized patients (35 per group) are thought to be enough to demonstrate a treatment difference of 3 hours with pooled standard deviation 3.5, between a single dose level of active treatment and control (i.e., 2.5 mg, 5 mg, or 7.5 mg mesdopetam vs placebo b.i.d.) for the primary endpoint with 92% power using a hierarchical testing strategy, with key secondary endpoints tested using a truncated Hochberg procedure with truncation parameter γ equal to 0.7 for the 7.5 and then the 5 mg doses and a standard Hochberg procedure for the 2.5 mg dose to maintain control of the family wise error rate (FWER) at the nominal 0.05 level.

QMD Ref: Worldwide-TMP-ST-005-7.0 Effective: 12Aug2019	Governing QMD: Worldwide-SOP-ST-001	
Confidentiality Statement		
This document is the property of Worldwide Clinical Trials Inc. and may not be duplicated, copied, altered or removed from company without prior approval from Worldwide Quality Assurance or in compliance with Worldwide Standard Operating Procedures.		
REF: Worldwide-TMP-QA-001f-1.3	Page 11 of 49	

Worldwide Clinical Trials Controlled Quality Management Document		
WORLDWIDE CLINICAL TRIALS	Sponsor:	Integrative Research Laboratories Sweden AB
	Protocol Number:	IRL790C005
STATISTICAL ANALYSIS PLAN. PHASE 2-3-4		

The sample size calculation was based on an expected dropout rate of 10%, i.e., assuming 31 patients per group will provide evaluable data on the primary endpoint at Week 12. The actual dropout rate was evaluated by the Sponsor after 70 randomized patients had completed Visit 3 (Week 4) and due to a higher-than-expected dropout rate, it was decided to increase the sample size to 154 (+10%) randomized patients as permitted by the protocol.

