6.1.4.1 CYP Genotype Subset

The CYP Genotype Subset will be a subset of the PK Analysis Set including patients who consented to genotyping with respect to CYP2D6 and who received a genotype classification result.

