6.16 Pharmacokinetic Analyses

Plasma concentrations of mesdopetam and its two main metabolites (IRL902 [N-dealkylated] and IRL872 [acetylated]) will be obtained pre-dose and 2 hours post-dose (as an estimate of C_{max}) at Visit 4 (Week 8) and Visit 5 (Week 12).

QMD Ref: Worldwide-TMP-ST-005-7.0 Effective: 12Aug2019	Governing QMD: Worldwide-SOP-ST-001	
Confidentiality Statement		
This document is the property of Worldwide Clinical Trials Inc. and may not be duplicated, copied, altered or removed from company without prior approval from Worldwide Quality Assurance or in compliance with Worldwide Standard Operating Procedures.		
REF: Worldwide-TMP-QA-001f-1.3 Page 2		

Worldwide Clinical Trials Controlled Quality Management Document		
WORLDWIDE CLINICAL TRIALS	Sponsor:	Integrative Research Laboratories Sweden AB
	Protocol Number:	IRL790C005
STATISTICAL ANALYSIS PLAN. PHASE 2-3-4		

Concentration data will be summarized by analyte, adjusted dose level, and visit at each scheduled sample time (nominal time) for the PK analysis set, using descriptive statistics. Line plots will also be provided showing mean (SD) by dose level and visit for each analyte.

In addition, concentration data will be summarized by genotype (poor, intermediate, normal, and ultrarapid metabolizer), adjusted dose level, and visit at each scheduled sample time (nominal time) using descriptive statistics and line plots for the CYP Genotype Subset.

All concentration data will be listed.

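### SAP 6.16 summarises concentrations by CYP2D6 genotype only within each dose level; a dose-normalised summary pooled over doses would be a cheap gain in precision for the rarer genotypes

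*SAP*

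**What the plan says.** SAP 6.16 states that "concentration data will be summarized by genotype (poor, intermediate, normal, and ultrarapid metabolizer), adjusted dose level, and visit" at each scheduled sample time, "using descriptive statistics and line plots for the CYP Genotype Subset". Four genotypes and three active doses make 12 groups at each visit and time. No concentration is divided by dose, no row combines doses and no genotype contrast is specified.

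The subset is defined in SAP 6.1.4.1 as "a subset of the PK Analysis Set including patients who consented to genotyping with respect to CYP2D6" and who received a classification. Footnote 3 of the protocol's study schedule adds: "Note: the CYP2D6 testing is optional". Protocol 9.4 says of the PK laboratory that "only samples taken from patients in the active group of the study will be analyzed".

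Two protocol statements bear on whether pooling is useful and reasonable. Section 8.2, on CYP2D6 and CYP1A2, says that "the exact contribution from each of these two enzymes in the elimination is not known" and introduces the genotyping in the same paragraph. Section 4.6 reports for phase 1 that "the PK evaluation in humans showed dose-linear kinetics with rapid absorption".

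Protocol 14.8 foresaw a power model of exposure on dose, if appropriate. SAP 6.16 does not contain it and SAP section 9 does not list its removal. No PK analysis described in SAP 6.16 therefore combines information across doses.

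**The concern.** The trial obtains a separate genetic consent and a blood sample, and the protocol names the role of CYP2D6 as an unresolved matter. The planned display divides the small number of patients with a less common genotype by three before anything is summarised. SAP 6.3.4 asks for a mean, SD and CV% in each group. An SD cannot be calculated from one patient and says very little from two or three.

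If kinetics are dose-linear, concentration divided by dose is comparable across the three arms, and pooling triples the number of patients behind each genotype estimate using data already collected. At stake is how precisely the report can describe exposure by genotype. The primary and key secondary efficacy analyses are not involved.

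**Working it through.** **Inputs from the documents.** Allocation is 1:1:1:1 with three active arms. SAP section 4 gives 35 randomised per group, 10% dropout and 31 evaluable per group at Week 12, later raised to 154 randomised in total.

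**Inputs not in the documents (assumed).** Genotype frequency 1 to 10%; consent 70 to 100%; between-patient CV 30 to 70%, with 50% as the central value; 16 normal metabolisers per dose (about half of 31), hence 48 over three doses.

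**Step 1: patients per dose.** The SAP's figure reproduces: 35 × 0.90 = 31.5, taken as 31. After the increase, 154 / 4 = 38.5 randomised per arm. The range of 31 to 38.5 per dose therefore assumes full consent, with the upper end also assuming no dropout. At 70% consent, 31 falls to 31 × 0.70 = 21.7.

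**Step 2: expected patients per cell** = patients per dose × genotype frequency; the pooled figure is three times that.

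| Assumed frequency | One dose (31 to 38.5) | Three doses pooled |
|---|---|---|
| 1% | 0.3 to 0.4 | 0.9 to 1.2 |
| 3% | 0.9 to 1.2 | 2.8 to 3.5 |
| 5% | 1.6 to 1.9 | 4.7 to 5.8 |
| 10% | 3.1 to 3.9 | 9.3 to 11.6 |

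At 70% consent (21.7 per dose) the one-dose figures run from 0.2 at 1% to 2.2 at 10%. Regrouping by adjusted dose moves dose-reduced patients down one level, so the three cells will not be equal. Splitting by visit and time does not reduce the number of patients, since the same patients are sampled again.

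**Step 3: chance of an empty or single-patient cell** (binomial, 31 per dose, 5%). P(0) = 0.95^31 = 0.20. P(1) = 31 × 0.05 × 0.95^30 = 0.33. P(at most 1) = 0.54 before rounding of the two parts. At 1%, P(0) = 0.99^31 = 0.73.

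**Step 4: precision of a geometric mean ratio.** With s = sqrt(ln(1 + CV²)), the 95% CI is the ratio multiplied and divided by exp(t(0.975, n1 + n2 − 2) × s × sqrt(1/n1 + 1/n2)). Example at CV 50%: s = sqrt(ln 1.25) = 0.472. For 2 v 16, the standard error is 0.472 × sqrt(1/2 + 1/16) = 0.354, t = 2.12, and the factor is exp(0.751) = 2.1. For 6 v 48, the standard error is 0.205, t = 2.01, and the factor is 1.5. Power is for a true two-fold ratio, two-sided 5%, from the noncentral t distribution.

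| Patients | CI factor at CV 30 / 50 / 70% | Power, two-fold, at CV 30 / 50 / 70% |
|---|---|---|
| 1 v 16, one dose | 1.9 / 2.8 / 4.0 | 57 / 27 / 17% |
| 2 v 16, one dose | 1.6 / 2.1 / 2.7 | 84 / 45 / 28% |
| 3 v 16, one dose | 1.5 / 1.9 / 2.3 | 94 / 59 / 38% |
| 3 v 48, pooled | 1.4 / 1.8 / 2.1 | 97 / 68 / 44% |
| 6 v 48, pooled | 1.3 / 1.5 / 1.7 | 100 / 91 / 70% |
| 9 v 48, pooled | 1.2 / 1.4 / 1.6 | 100 / 98 / 84% |

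For a three-fold ratio at CV 50%, power within one dose is 56%, 83% and 94% with 1, 2 and 3 patients.

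**The case against.** A reader might infer that the rarer cells will hold one to three patients and so cannot show whether CYP2D6 status changes exposure. The documents do not support that. They give no genotype frequency, consent rate or PK variability. An expected count of one to three per cell needs a frequency of about 3.2 to 9.7% with 31 per dose (1/31 to 3/31), and rarer genotypes would mostly give empty cells. Nor is the display uninformative: a three-fold difference could be visible within one dose, and at a CV of 30% two or three patients would often suffice for a two-fold one. The three doses will also be read side by side.

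A reader might also put a confidence interval on a single two-patient cell, which at CV 50% spans a factor of about 70 either way. That figure misleads, because it estimates the variance from those two patients alone. The useful quantity is a ratio to normal metabolisers, where the change from 2 v 16 to 6 v 48 is from about 2.1 to 1.5.

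Three further points stand. No objective or endpoint concerns CYP2D6. All concentrations and genotypes are listed, and SAP section 6 allows extra tables in the report, so a pooled look remains possible; but the normalisation and reference group would then be chosen after the data are seen. Pooling also has limits. The reported dose-linearity comes from healthy men at single doses of 5 to 120 mg and at 40 or 80 mg per day, and the statement does not name the metabolites. Protocol 8.2 excludes only the combination of strong CYP1A2 and CYP2D6 inhibitors, so a patient on one strong CYP2D6 inhibitor may have less enzyme activity than the genotype suggests. SAP 6.3.4 sets values below the limit of quantification to zero, which has no logarithm. These points shape the remedy but do not remove the gain in precision.

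**Conclusion.** The point holds as a cheap improvement. The plan has no dose-normalised genotype summary pooled over doses, and for any genotype at an assumed 1 to 10% the by-dose cells are expected to hold 0 to 4 patients. At a CV of 50%, power for a two-fold difference is 27 to 59% within one dose with one to three patients, against 68 to 98% with three times as many pooled. The size of the gain depends on the assumed frequency and CV: it is smaller at 30%, and at 70% even the pooled estimate is imprecise with three patients. A pooled ratio would describe exposure by genotype more precisely; it would not by itself settle how much CYP2D6 contributes to elimination. The matter is minor and descriptive, and leaves efficacy inference untouched.

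**What to change.** Add to SAP 6.16 a summary of dose-normalised parent mesdopetam at trough and at 2 hours (concentration divided by the dose in use at sampling), pooled over dose levels, by genotype and visit. Give geometric mean ratios of poor, intermediate and ultrarapid to normal metabolisers with 95% CIs. With it:

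- state a rule for values below the limit of quantification that works on the log scale, in place of zero, for this summary;
- identify patients taking a strong CYP2D6 inhibitor at sampling, so that their values can be recognised;
- keep the planned by-dose table as the check on dose linearity, because phase 1 tested no dose below 5 mg and one arm here takes 2.5 mg b.i.d.

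The cost is a small set of extra tables (two sample times, two visits, three ratios) and reliance on dose linearity for the pooled figures. No new data or patient procedures are needed.

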6.17 Safety Analyses

Safety analyses will be presented by actual treatment group as well as adjusted dose group for all patients in the SAS.

6.17.1 Adverse Events

Adverse events will be collected from the time of informed consent and continues through the last follow-up assessment in the study.

A treatment emergent adverse event (TEAE) is defined as:

- Any AE that has an onset on or after the first dose of study drug through the last follow-up assessment in the study.
- Any pre-existing AE that has worsened in severity on or after the first dose of study drug through the last follow-up assessment in the study.

A treatment-related AE is defined as an AE relationship to study drug classified by the Investigator as 'possible', or 'probable'. If an AE has missing relationship, 'probable' will be assumed for analysis purposes.

Severity of the AE will be graded using the Common Terminology Criteria for Adverse Events (CTCAE) grading system (Version 5.0): Grade 1 (Mild), Grade 2 (Moderate), Grade 3 (Severe), Grade 4 (Life-Threatening), Grade 5 (Fatal). Grade 3 (Severe) will be assumed for an AE with missing grade.

An overall summary table of AE incidence (number and percent of patients) and number of events, will be presented by treatment group and overall, for the following categories:

Any Reported TEAE

 QMD Ref: Worldwide-TMP-ST-005-7.0 Effective: 12Aug2019
 Governing QMD: Worldwide-SOP-ST-001

 Confidentiality Statement

 This document is the property of Worldwide Clinical Trials Inc. and may not be duplicated, copied, altered or removed from company without
 prior approval from Worldwide Quality Assurance or in compliance with Worldwide Standard Operating Procedures.

 REF: Worldwide-TMP-QA-001f-1.3
 Page 42 of 49

- **Treatment-Related TEAEs**
- Serious TEAEs
- Serious Treatment-Related TEAEs
- TEAEs Leading to Reduction in Dose of Study Drug
- TEAEs Leading to Interruption of Study Drug
- TEAEs Leading to Withdrawal of Study Drug
- TEAEs Leading to Early Withdrawal from Study •
- **TEAEs** Leading to Death •

Summaries of TEAE incidence and number of events by SOC and PT will be presented by treatment group and overall, for the following:

- TEAEs
- Treatment-related TEAEs •
- Serious TEAEs
- Serious Treatment-Related TEAEs
- TEAEs by Maximum Grade, (incidence only)
- Treatment-Related TEAEs by Maximum Grade, (incidence only)
- TEAEs by Strongest Relationship, (incidence only)
- Treatment-Related TEAEs by Strongest Relationship, (incidence only)

The following listings of AEs will be presented in Section 14.3.2 of the CSR:

- Serious AEs
- TEAEs Leading to Interruption of Study Drug
- TEAEs Leading to Withdrawal of Study Drug
- TEAEs Leading to Early Termination from Study
- Deaths

TEAE tabulations will be presented by SOC and PT in descending frequency of AE incidence in the pooled mesdopetam arm and then alphabetically for ties.

All reported AEs will be listed in Appendix 16.2.7 of the CSR with separate listings for TEAE and non-treatment-emergent AEs (NTEAE).

Overall ongoing TEAEs will be summarized by month 1, 2, and 3. Additionally, TEAEs that occur in >5% of all participants will be summarized by month 1, 2, and 3.

QMD Ref: Worldwide-TMP-ST-005-7.0 Effective: 12Aug2019	Governing QMD: Worldwide-SOP-ST-001		
Confidentiality Statement			
This document is the property of Worldwide Clinical Trials Inc. and may not be duplicated, copied, altered or removed from company without prior approval from Worldwide Quality Assurance or in compliance with Worldwide Standard Operating Procedures.			
REF [·] Worldwide-TMP-OA-001f-1 3	Page $43 \text{ of } 49$		

Worldwide Clinical Trials Controlled Quality Management Document		
WORLDWIDE CLINICAL TRIALS	Sponsor:	Integrative Research Laboratories Sweden AB
	Protocol Number:	IRL790C005
STATISTICAL ANALYSIS PLAN. PHASE 2-3-4		

